Describe in detail the methods and procedures that will be used to accomplish the objectives and specific aims of the project. Discuss the alternative methods that are available and justify the use of the method proposed in the study. Justify the scientific validity of the methodological approach (biomedical, social, or environmental) as an investigation tool to achieve the specific aims. Discuss the limitations and difficulties of the proposed procedures and sufficiently justify the use of them. Discuss the ethical issues related to biomedical and social research for employing special procedures, such as invasive procedures in sick children, use of isotopes or any other hazardous materials, or social questionnaires relating to individual privacy. Point out safety procedures to be observed for protection of individuals during any situations or materials that may be injurious to human health. The methodology section should be sufficiently descriptive to allow the reviewers to make valid and unambiguous assessment of the project. **(DO NOT EXCEED TEN PAGES, USE CONTINUATION SHEETS).**

Design: This is a randomized, controlled, home-based intervention study.

Patients selection: Children attending the out-patient department of ICDDR,B hospital will be considered for selection into the study.

Inclusion criteria:

- a) Age 5 months to 36 months
- b) Duration of diarrhoea > 14 days
- c) Dehydration status-some or nil according to WHO criteria
- d) Written informed consent obtained from parents or legal guardian
- e) Accessible distance (within 15 km radius from ICDDR,B)

Exclusion criteria:

- a) Signs of systemic illness or other severe illnesses requiring hospital-based care (sepsis, severe pneumonia, meningitis, severe hyponatraemia or hypokalaemia)
- b) Severe malnutrition - wt/age <60% with or without edema.
- c) Patients with severe dehydration
- d) Bloody diarrhoea

Observation period:

All patients attending the outpatient department of ICDDR,B from 8 a.m. to 2 p.m. with history of persistent diarrhoea will be screened for eligibility for this study following the inclusion and exclusion criteria. The children who are eligible will initially be observed for 4 hours. A detailed clinical history will be recorded, and physical examination including anthropometry will be done. Children with some dehydration will be rehydrated with WHO-ORS.

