At home, care-givers will record on a diarrhoea diary the frequency of stool each 24 hours, the stool consistency and time of cessation of diarrhoea. (Definitions below). After 7 days if diarrhoea continues, caregivers will be trained to prepare Diet B and will be instructed to feed Diet B - a milk free diet containing rice-cereal, vegetable oil, egg albumin and glucose mixture. The second diet (B) will also be fed for 7 days. For partially breastfed children the diets will be offered to attain energy intake >75 kcal/kg/day and for non-breastfed child the energy intake will be 110 kcal/kg/day. In addition multivitamin drops and zinc acetate are standard therapy for PD patients and will be given routinely to all children from the beginning of the study and for the following three weeks (Table 2). The dosage of multivitamin syrup will be 1 ml twice daily and Zinc acetate 10 mg twice daily. Oral rehydration with standard WHO-ORS will continue to maintain hydration to replace ongoing liquid stool losses until cessation of diarrhoea. The number of ORS packets used will be recorded.

On day 7 after beginning of diet A, if the patients are found to have normal stool (soft or formed), they will continue diet A.

After 7 days of second dietary regime, if diarrhoea persists, the patients will be admitted to the inpatient department for further evaluation and management according to the standard hospital practice at ICDDR,B.

Control group

The patients under control group will receive standard management which is advised to take WHO-ORS at home for maintenance of hydration and to continue his/her usual diet or as advised by hospital physician.

Follow-up:

All patients will be followed-up by home visits on every alternate day up to day 15 and then every 2 weeks thereafter up to 4 weeks. The children will be examined thoroughly including anthropometry at every follow up. Study personnel will also monitor the preparation of diet at home. Samples of prepared diet will also be collected and stored in deep freezer for quality study (e.g. composition and calories).

Fig. 1

DIETARY TREATMENT ALGORITHM

[figure not shown]

Table 1. Composition of study diets

Diet A		Diet B	
Milk/Suji/Litre (>4 mo age group)		Full-Strength Rice Suji/L	
Whole milk powder	40 g	Rice powder	60 g
Rice powder	40 g	Egg white	100 g (four)
Sugar	25 g	Oil (Soya)	30 ml
Oil (Soya)	25 g	Glucose	35 g
Mag. Chloride	0.5 g	Kcl	01 g
Potassium chloride	01 g	Mag. Chloride	0.5 g
Calcium	02 g	Calcium	02 g

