After cooked volume	1000 ml	After cooked volume	1000 ml
Energy	67kcal/100ml	Energy	70 kcal/100 ml
Protein	4.4 gm/100ml	Protein	1.88 g/100 ml
PER*	8%	PER	10%

Table 2. Composition of Multivitamin drop (Composition per 1 ml)

Vitamin A U.S.P.	5000 IU
Vitamin D B.P.	640 IU
Ascorbic Acid (C) B.P.	50 mg
Thiamine Hcl (B ₁)	1.6 mg
Riboflavin Sodium Phosphate (B ₂) B.P.	1.37 mg
Pyridoxine B.P. (B ₆) U.S.P.	1.0 mg
Nicotinamide B.P.	10.0 mg
D-Panthenol U.S.P.	5.0 mg
Folic acid	0.25 mg

Justification of selection of diet A in the beginning

Dietary treatment algorithm is a well recognised treatment schedule for the nutritional management of children suffering from persistent diarrhoea. In ICDDR hospital, this treatment algorithm is also being followed. Justification of using Diet A initially is that this diet is easy to prepare, culturally acceptable, less modified as compared to Diet B. and less expensive (1 L Diet A costs Tk. 18.00 vs. Tk. 26.00 for Diet B).

Study withdrawal

Patients will be considered withdrawn from the study if a) their parents withdraw informed consent, or b) needs hospital care.

Patients will be considered for hospital care for the following reasons:

a) appearance of signs of some dehydration b) signs of severe infections (e.g. fever, cough, respiratory distress, tachycardia, tachypnoea, reluctant to feeding etc. c) signs of electrolyte imbalance (e.g. less responsive to environments or irritability, abdominal distensions etc.). After hospitalisation, the patients will be managed according to the standard hospital practice. Patients will be followed up even after withdrawn from the study. Data obtained from the withdrawn patients will also be included in the analysis upto the time of withdrawal.

Sample size

Sample size was calculated on the basis of two major outcome variables:

- a) success rate of diet therapy
- b) Growth faltering (percentage of patients experiencing weight loss during the study periods).

Based on the study (21) the sample size of this study is determined to be of 137 in each group on anticipated success rate (combining success of Diet A and Diet B) of 80% in the intervention group against an arbitrary standard success rate of 65% in the control group, considering a significance level of 5% and power of 80%. Assuming a dropout of 15%, a total sample of 320 patients was calculated.

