We are not expecting significant difference in recovery rate on diet A and the control. However, if the difference is 20% or more, then the present sample size will be enough to detect the significant difference.

Thirty percent of children under control group is anticipated to experience weight loss as opposed to 10% in the intervention group during the study periods. Considering a significance level of 5% and 80% power, the sample size in each group is calculated as 60.

Finally, we consider the total sample size for this study as 320.

Organization of the trial

Patients attending in the treatment centre of ICDDR,B will be evaluated for recruitment for study.

Study Schedule

The study will be started after the approval of RRC and ERC and allocation of budget. The first two months will be utilized for staff recruitment, training and pretrial. 20 months will be needed for patients study. Last 2 months will be utilized for data analysis and reporting of the study results.

Definition

Diarrhoea: Three or more abnormal stools (loose or watery) during a 24-hour period.

Stool consistency: Abnormal stool - loose/watery or abnormal as considered by mother.
Normal stool - soft/formed or normal as considered by mother.

Cessation of diarrhoea: Last abnormal stool followed by normal stool at least for three days.

Success of diet therapy: Cessation of diarrhoea within 7 days of starting of the modified diet (diet A or diet B).

Facilities Available

Describe the availability of physical facilities at the place where the study will be carried out. For clinical and laboratory-based studies, indicate the provision of hospital and other types of patient's care facilities and adequate laboratory support. Point out the laboratory facilities and major equipments that will be required for the study. For field studies, describe the field area including its size, population, and means of communications. (TYPE WITHIN THE PROVIDED SPACE).

ICDDR,B treatment centre will be used for patients recruitment, observation, and training of the caregivers of the patients.

Data Analysis

Describe plans for data analysis. Indicate whether data will be analyzed by the investigators themselves or by other professionals. Specify what statistical softwares packages will be used and if the study is blinded, when the code will be opened. For clinical trials, indicate if interim data analysis will be required to monitor further progress of the study. (TYPE WITHIN THE PROVIDED SPACE).

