Statistical analysis

Statistical analysis will be done using SPSS/PC software. Percentage of success of treatment for each dietary intervention and overall success rate will be calculated. Relative risk ratios and their associated 95% confidence intervals will be calculated to identify variables (e.g. inappropriately making and feeding the diet, associated other infections, education of mothers, family income, no. of children in the family, source of drinking water, antibiotic use before admission, type of dehydration before intervention, frequency of stool etc.) that were related to the treatment failure. Overall success rate (the number of patients recovered at the end of 10 days) in the intervention group will be compared with that of control group. The number of patients lost weight will also be compared between the groups.

Adjusted analysis will be done by constructing life tables of the two groups and will be compared by log rank test.

Ethical Assurance for Protection of Human Rights

Describe in the space provided the justifications for conducting this research in human subjects. If the study needs observations on sick individuals, provide sufficient reasons for using them. Indicate how subject's rights are protected and if there is any benefit or risk to each subject of the study.

This intervention study will be conducted among the children under 5 years of age because these children are the sufferers from this illness of persistent diarrhoea. Written informed consent will be duly signed by the parents or legal guardians.

There is no risk for this intervention on the other hand they might be benefited from this intervention.

Use of Animals

Describe in the space provided the type and species of animal that will be used in the study. Justify with reasons the use of particular animal species in the experiment and the compliance of the animal ethical guidelines for conducting the proposed procedures.

Not applicable.

Literature Cited

Identify all cited references to published literature in the text by number in parentheses. List all cited references sequentially as they appear in the text. For unpublished references, provide complete information in the text and do not include them in the list of Literature Cited. There is no page limit for this section, however exercise judgment in assessing the "standard" length.

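### The malnutrition exclusion can admit oedematous children at or above 60% weight-for-age, and the weight-loss outcome may then count some who improve as faltering

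*Protocol*

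**What the plan says.** **Entry.** Exclusion criterion b) in Research Design and Methods is "Severe malnutrition - wt/age <60% with or without edema". Criterion a) is "Signs of systemic illness or other severe illnesses requiring hospital-based care (sepsis, severe pneumonia, meningitis, severe hyponatraemia or hypokalaemia", closed by a bracket. No other criterion names oedema.

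**Outcome.** Under Sample size: "Sample size was calculated on the basis of two major outcome variables". The second of these is "Growth faltering (percentage of patients experiencing weight loss during the study periods", closed by a bracket. Under Statistical analysis: "The number of patients lost weight will also be compared between the groups". Neither place sets a minimum loss, says which two weights are compared, or makes an exception for oedema.

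**Measurement.** Under Follow-up, home visits take place on alternate days to day 15 and then every 2 weeks up to 4 weeks, and "The children will be examined thoroughly including anthropometry at every follow up". A physical examination with anthropometry is also planned during the observation period at entry.

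**Planning figures.** "Thirty percent of children under control group is anticipated to experience weight loss as opposed to 10% in the intervention group". "Considering a significance level of 5% and 80% power, the sample size in each group is calculated as 60". The success outcome is planned at 80% v 65% with 137 per group. The total of 320 allows for 15% dropout.

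**The concern.** Criterion b) turns on weight alone. Retained fluid adds to measured weight, so weight-for-age is least informative in a child with oedema, and such a child may sit at or above the cut-off. The wording makes oedema irrelevant below 60% and says nothing about it above.

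The growth outcome then reads any fall in weight as deterioration. For a child who entered with oedema, a net fall may mean that fluid has cleared, which is improvement.

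Randomisation balances the number of such children on average. It does not balance how often their oedema clears. If clearance is more frequent in the better-fed arm, false faltering accumulates there and the difference between arms shrinks. At stake are the correct classification of individual children and the size of the estimated effect on one of the two outcomes the trial was sized on.

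**Working it through.** **1. The plan's own figure.** Inputs: 30% v 10%, 5% significance (taken as two-sided; the protocol does not say), 80% power.

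- Unpooled formula: n = (1.96 + 0.84)² × (0.30×0.70 + 0.10×0.90) / 0.20² = 58.9, so 59 per group.
- Arcsine formula: 59.0, or 60 rounded up. Pooled-variance formula: 62.

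The stated 60 per group reproduces.

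**2. Children available for this outcome.** 320 × 0.85 = 272, or 136 per arm. With 30% v 10% and no oedematous entrants, power is 98.7% (pooled-variance test).

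**3. Illustration with oedematous entrants.** The protocol gives neither their share e nor any clearance rate. Assumptions:

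- e is the same in both arms.
- The success rates (80% and 65%), which measure cessation of diarrhoea, stand in for clearance of oedema.
- Every child whose oedema clears has a net weight loss.
- All other children, including those whose oedema does not clear, lose weight at the planned 10% or 30%.

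Formulas:

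- Intervention: 10%(1 − e) + e(80% + 20%×10%) = 10%(1 − e) + 82%e
- Control: 30%(1 − e) + e(65% + 35%×30%) = 30%(1 − e) + 75.5%e

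| e | Intervention | Control | Contrast | Power, 136 per arm |
|---|---|---|---|---|
| 0 | 10.0% | 30.0% | 20.0 points | 98.7% |
| 5% | 9.5 + 4.1 = 13.6% | 28.5 + 3.775 = 32.3% | 18.7 points | 96.0% |
| 10% | 9.0 + 8.2 = 17.2% | 27.0 + 7.55 = 34.6% | 17.4 points (17.35) | 90.9% |

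Power at e = 5%, as an example: the mean proportion is (0.136 + 0.32275)/2 = 0.2294. The standard error is 0.0510 under no difference and 0.0497 under the alternative. Then z = (0.18675 − 1.96×0.0510)/0.0497 = 1.75, which gives 96.0%.

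The ratio of the two rates moves from 0.33 to 0.42 at e = 5% and 0.50 at e = 10%.

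**4. Other clearance patterns.**

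- All oedematous children in both arms lose weight: 14.5% v 33.5% at 5% (power 96.0%) and 19.0% v 37.0% at 10% (91.5%).
- Extreme case, in which every oedematous child in the intervention arm loses weight and no oedematous control does: 14.5% v 28.5% at 5% (80.6%) and 19.0% v 27.0% at 10% (34.7%). Nothing in the protocol suggests a split that sharp; it marks the outer bound.

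**The case against.** Several objections have force.

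- **Net weight need not fall.** Intervention children who are not breastfed are to receive 110 kcal/kg/day, follow-up runs to 4 weeks, and the two weights to be compared are not fixed. Tissue gain may offset fluid loss. This stands: misclassification is possible, not certain.
- **The clearance rates are borrowed.** The 80% and 65% are rates of diarrhoea cessation, and nothing in the protocol ties them to oedema. This stands too, and the table is illustrative only.
- **Such children may be few.** The protocol targets non-severe cases, every child is examined and observed for 4 hours, and criterion a) lets a screener exclude for severe illness needing hospital care. That may lower e. It does not settle the point, because the examples in a) do not mention oedema or malnutrition and its use here is discretionary.
- **Handling may be in an analysis plan that is not shown.** The scoring rule could be there. But the protocol itself fixes both the entry criterion and the any-loss definition, and it is their combination that can misclassify.

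A reader might infer something stronger: that recovery is scored as failure for these children as a rule, or that the weight comparison loses its power. The documents support neither. No passage says that oedema clears or weight falls under either regimen, and the illustration keeps power above the planned 80%. Only the extreme split at e = 10% takes power well below that. Nor does the text contradict itself; criterion b) is incomplete for this outcome.

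**Conclusion.** The point holds in conditional form. As written, criterion b) does not bar a child with oedema at or above 60% weight-for-age, and the any-loss definition may count such a child as faltering while improving. If oedema clears more often in the better-fed arm, the weight comparison is biased towards no difference.

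Under the stated assumptions the loss is about 1.3 points of the planned 20 at e = 5% and about 2.65 at e = 10%. If oedema is rare at entry, the effect is negligible. The conclusion about direction rests on differential clearance; the size rests on an unknown e and on borrowed clearance rates. The main harm is misclassification and a diluted effect on a major outcome, which is worth a one-line correction.

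**What to change.** 1. Record presence or absence of oedema at the entry examination already planned. State that children with oedema at entry are left out of the weight-loss comparison in both arms. The rule depends only on baseline status, so the randomised comparison is kept among the children who remain. Counting from the first oedema-free weight is less suitable, because that starting point falls after randomisation and can differ by arm.
2. Reconcile the wording of criterion b) with the non-severe target population and the weight-loss outcome, and state whether oedema at or above 60% weight-for-age was meant to exclude. Which entry rule is right is for the sponsor; none is proposed here.

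**Cost.** One recorded item and one sentence, with no new procedure. The weight-loss result then applies to children without oedema at entry, and slightly fewer are analysed: 136 × 0.95 = 129 per arm at e = 5% (power 98.3% for 30% v 10%) or 136 × 0.90 = 122 at e = 10% (97.8%). Both are well above the 60 per group the protocol asks for.

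### The protocol provides for no stool record in the control arm, and its powered success outcome has no time origin for controls and conflicts with the 10-day rate compared between arms

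*Protocol*

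**What the plan says.** **Stool record.** In Case management, under Intervention group: "At home, care-givers will record on a diarrhoea diary the frequency of stool each 24 hours". Consistency and the time at which diarrhoea stops are to be entered too. This is the only instruction to record stools.

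**Control group.** "The patients under control group will receive standard management which is advised to take WHO-ORS at home for maintenance of hydration", together with the usual or physician-advised diet. No diary or stool history is mentioned.

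**Follow-up, all patients.** "All patients will be followed-up by home visits on every alternate day up to day 15 and then every 2 weeks thereafter up to 4"; the final figure is in weeks. On content: "The children will be examined thoroughly including anthropometry at every follow up". Monitoring of diet preparation and diet samples are added, but no stool record.

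**Outcome definitions.**
- Definition section: cessation is a final abnormal stool and then at least three days of normal stool, with no arm named. Success of diet therapy is "Cessation of diarrhoea within 7 days of starting of the modified diet (diet A or diet B").
- Sample size section: 80% success in the intervention arm, pooling the two diets, against an arbitrary 65% in controls. No window is attached to the 65%.
- Statistical analysis section: the overall success rate, there a 10-day recovery count, "in the intervention group will be compared with that of control group". Life tables of the two groups are compared by log-rank test.

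**The concern.** Success of diet therapy is one of the two outcomes that set the sample size. To compare it fairly, the same instrument and the same clock are needed in both arms, and the text secures neither.

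Staff who follow the document literally have no instruction to give control caregivers a diary. Cessation could then come from a daily prospective record in one arm and from recall at alternate-day visits in the other. Caregivers know the allocation, because diet ingredients go to one arm only, and stool may be classed as normal or abnormal on the mother's own judgement. In that setting a difference in recording could pass for a difference in diet.

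The formal success definition also cannot be computed for a control child, who never starts a study diet. The success comparison and the log-rank test would both be affected. An analysis plan cannot recover daily records that were never collected.

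**Working it through.** **1. The plan's own figure.** Inputs from Sample size: 80% v 65%, 5% significance (taken as two-sided), 80% power.

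Pooled variance: n = [1.96√(2 × 0.725 × 0.275) + 0.842√(0.80 × 0.20 + 0.65 × 0.35)]² / 0.15² = (1.238 + 0.524)² / 0.0225 ≈ 137.9, so 138 per arm. The unpooled form gives 135.2, so 136. The stated 137 is reproduced. For 15% dropout, 274/0.85 = 322 and 274 × 1.15 = 315; the stated 320 lies between. With 160 × 0.85 = 136 left per arm, power is 79.4%. The sample size is not wrong on its own inputs.

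**2. Where stool recording is provided for**

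| Place in protocol | Stool record? | Applies to |
|---|---|---|
| Case management, Intervention group | Daily diary | Arm not named; heading is intervention |
| Control group | None mentioned | Controls |
| Follow-up | None mentioned | All patients |
| Definition, cessation | Needs the last abnormal stool and three normal days | Arm not named |

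The sentence before the diary instruction limits supply of diet ingredients to the intervention arm. The one after it concerns training for Diet B. Both neighbours are intervention-only.

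The alternate-day visits end at day 15 and the next visit is two weeks later, about day 29. If a child's last abnormal stool is on day 14, the three normal days are days 15 to 17. Without a diary they could be confirmed only at about day 29, from memory.

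**3. Which clock applies**

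| Section | Window | Origin | Usable in controls? |
|---|---|---|---|
| Definition | 7 days per diet | Start of Diet A or B | No |
| Sample size | Two 7-day diets pooled, 7 + 7 = 14 days | Start of Diet A, by implication | None given for the 65% |
| Statistical analysis | 10 days | Not stated | Yes, once an origin is set |

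A 10-day cut falls 10 − 7 = 3 days into Diet B, so it matches neither the 7-day rule nor the 14-day sequence behind the 80%.

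**4. Illustration of timing.** These assumptions are not in the protocol: exponential recovery, and 65% recovered at 14 days. Hazard = −ln(0.35)/14 = 0.0750 per day.
- 7 days: 1 − exp(−0.0750 × 7) = 40.8%
- 10 days: 1 − exp(−0.0750 × 10) = 52.8%
- 14 days: 65.0%

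If both arms followed this curve, counting the intervention arm over 14 days and controls over 10 or 7 would show a gap of 12.2 or 24.2 points with no diet effect. The planned difference is 15 points.

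**5. Illustration of ascertainment.** The error rates are assumed, with 136 per arm.

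True success 65% in both arms, with a share m of control recoveries missed, so that recorded control success is 0.65 × (1 − m):

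| m | Recorded control success | Chance of significance favouring intervention (nominal 2.5%) |
|---|---|---|
| 5% | 61.75% | 8% |
| 10% | 58.5% | 20% |
| 15% | 55.25% | 38% |
| 20% | 52.0% | 59% |

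In the other direction, with intervention success 80%, if control success is recorded as 68%, 70% or 72% instead of 65%, power falls from 79% to 62%, 48% or 34%.

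**The case against.** A reader might infer that the diary is scheduled only in the intervention arm, and that the main outcome is neither measured nor defined in controls. The document does not support that.

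- The diary sentence names no arm. The same section holds procedures for everyone: vitamins and zinc "will be given routinely to all children from the beginning of the study", and alternate-day house visits stated there without an arm label, which Follow-up shows to cover all patients. Placement under a heading therefore does not prove exclusivity.
- Control children are visited every second day to day 15, and a caregiver asked about the days since the last visit can account for each of them.
- Cessation is defined without reference to arm, and the 10-day rate in Statistical analysis can be applied to controls.
- The 7-day rule can be read as a per-diet description, since Statistical analysis reports success for each diet separately from the overall rate.

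It is also tempting to claim that alternate-day visits delay recorded control recovery by about a day and so cost controls a few points. Cessation is dated by the last abnormal stool, not by the visit. Even with visit dating, visits on days 3, 5, …, 15 are 2, 4, …, 14 days after day 1, so a window of 10 or 14 elapsed days ends on a visit and loses no recovery.

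These points remove the stronger reading. What stands is that no text provides for a stool record in controls, the 10-day rate has no origin, and the outcome used for the sample size is worded so that it cannot be applied to controls.

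**Conclusion.** The concern holds in limited form. The protocol does not provide for the stool diary in the control arm. Its powered success definition has no time origin for controls and conflicts with the 10-day rate that is to be compared. Read literally, an outcome partly judged by mothers who know the allocation could be ascertained and timed differently by arm.

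Neither the size nor the direction of any bias can be derived from the protocol. The illustrations rest on assumed recovery curves and error rates. They show only that mismatches of plausible size would matter against a 15-point difference, and that they could either create a false effect or hide a real one. The sample size arithmetic is sound. What is unclear is which outcome and which window the 80% and 65% describe.

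**What to change.** - **Diary.** State in Follow-up that caregivers in both arms keep the same daily diarrhoea diary from day 1, checked at each home visit, and continue it long enough to confirm three normal days after the end of the success window.
- **Clock.** Reconcile Sample size, Definition and Statistical analysis. The between-group success rate and the life tables should use one window counted from randomisation in both arms, and it should be the window to which the 80% and 65% refer. If the 10-day window is kept, those two rates need to be justified at 10 days, because the 80% pools two 7-day diets.
- **Per-diet success.** Keep the 7-days-per-diet definition only as a description within the intervention arm.

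The cost is diary forms and brief instruction for control caregivers, whose homes are already visited every second day. Keeping a diary may sharpen attention to stools, but equally in both arms. No treatment changes.

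### Children who need hospital care contribute data only up to withdrawal although they are still followed, so later weights of the sickest children are left out of the weight-loss comparison (minor)

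*Protocol*

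**What the plan says.** Protocol, *Study withdrawal*, gives three linked rules:

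- On who is withdrawn: "Patients will be considered withdrawn from the study if a) their parents withdraw informed consent, or b) needs hospital care".
- On what happens to them next: "Patients will be followed up even after withdrawn from the study".
- On how their records are used: "Data obtained from the withdrawn patients will also be included in the analysis upto the time of withdrawal".

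Under "Patients will be considered for hospital care for the following reasons" the section lists signs of some dehydration, of severe infection and of electrolyte imbalance. The list applies to both arms.

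*Follow-up* says that all patients are "followed-up by home visits on every alternate day up to day 15 and then every 2 weeks thereafter up to 4 weeks". On what is done at those visits it says: "The children will be examined thoroughly including anthropometry at every follow up".

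*Case management, Intervention group* contains a further step: "After 7 days of second dietary regime, if diarrhoea persists, the patients will be admitted to the inpatient department for further evaluation and management". The *Control group* paragraph has no matching step; those children take ORS and "continue his/her usual diet or as advised by hospital physician".

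*Sample size* names growth faltering, the percentage losing weight over the study periods, as one of two major outcomes (30% control, 10% intervention). *Statistical analysis* compares the number who lost weight between the groups. Neither section fixes a day for that weight.

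**The concern.** A child who becomes ill enough for hospital is the child whose weight is most in doubt. Under the withdrawal rule that child's weight record ends, for analysis, at that moment, although follow-up goes on. The cut is therefore not random. It is triggered by clinical deterioration, and one trigger, some dehydration, can be a direct consequence of the diarrhoea being treated.

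The rule is worded the same for both arms, but equal wording does not give equal frequency. If the diet shortens diarrhoea, fewer intervention children may be cut off; if it is badly tolerated, more may be. Either way, the arms would be compared on records that stop early for different numbers of sick children. This touches one of the two outcomes on which the trial is sized.

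A second issue arises only if weights after about day 14 enter the comparison. Admission for diarrhoea that outlasts Diet B is then a route into hospital that is written for one arm.

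**Working it through.** **1. The plan's own figure.** Inputs from *Sample size*: 30% v 10%, 5% significance (two-sided assumed, since the sides are not stated), 80% power.

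- Pooled variance: n = [1.96√(2·0.20·0.80) + 0.842√(0.30·0.70 + 0.10·0.90)]² / 0.20² = 61.6, so 62.
- Unpooled variance: n = (1.96 + 0.842)²(0.21 + 0.09) / 0.20² = 58.9, so 59.

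The plan says 60. For 80% v 65% the same formulas give 138 and 136; the plan says 137. The sizing reproduces and is not disputed.

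**2. The withdrawal rules side by side.**

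| Rule | Effect on weights |
|---|---|
| Need for hospital care means withdrawal | Can occur on any day, in either arm |
| Follow-up continues after withdrawal | Later weights can be collected |
| Anthropometry at each follow-up | Weighing is already planned |
| Analysis only up to withdrawal | Those later weights are discarded |

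The first three rules arrange for the data, and the fourth excludes them.

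**3. Size.** Let w be the share of an arm withdrawn for hospital care, and f the share of these whose weight-loss status differs with and without the later weights. The arm's weight-loss percentage shifts by w × f. The size of the distortion in the difference between arms is |w_I·f_I − w_C·f_C|, which vanishes if the products are equal. The protocol gives neither w nor f.

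- One child in 137 is 1/137 = 0.73 points.
- The planned difference of 20 points is 0.20 × 137 = 27 children.
- Illustration on an assumed net imbalance of 1 to 5 children between arms: 0.7 to 3.6 points (5/137 = 3.6%).

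**4. Direction.** If weight loss means any loss below baseline at any visit, cutting a record can only remove events, and the arm with more cut records gains. If it means last weight against baseline, the cut can also hide later regain, and the sign can reverse. The protocol does not say which is meant, so the direction is open.

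**5. The admission step.** Diet A takes days 1 to 7 and Diet B days 8 to 14. Alternate-day visits, starting from the day 3 visit named in the protocol, fall on days 3, 5, 7, 9, 11, 13 and 15. Days 3 to 13 come before any admission under this step; only day 15 and later weighings are exposed. At the planned 80% success, at most 0.20 × 137 = 27 intervention children would reach the step; at 65%, at most 0.35 × 137 = 48. These are upper limits at those rates, because some failures leave earlier under the common criteria. They count children reached by the step and do not estimate bias.

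**6. Power if day 15 becomes the weight endpoint** (137 per arm, two-sided 5%, pooled-variance normal approximation; the fraction of the effect seen by day 15 is an assumption):

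| Effect seen by day 15 | Rates | Power |
|---|---|---|
| All | 30% v 10% | 99% |
| Two thirds | 20% v 6.7% | 90% |
| Half | 15% v 5% | 79% |

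**The case against.** **The withdrawal rule is symmetric.** It applies to both arms, so the bias may be small or may cancel. That stands as a limit on size. It does not justify discarding weights that the plan already collects.

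**The analysis plan can settle it.** This holds for the assessment day, which is not treated here as an omission. It does not hold for the cut-off at withdrawal, which the protocol states; an analysis plan that used later weights would contradict it.

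**The admission step.** A reader might infer that all weights after about day 14 are not comparable between arms, or that a positive weight result could be produced by inpatient care alone. The documents do not support that, for four reasons:

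- The protocol never says that the weight comparison uses weights after day 14. If the study periods are the two diet weeks, the step has no effect.
- The step stands under the intervention group's treatment algorithm and can be read as its last stage. Later weights then belong to the strategy being compared. The figure of the algorithm is not available to settle this.
- Persisting diarrhoea is not among the listed reasons for hospital care, so it is not stated that this admission counts as withdrawal.
- Nothing bars admission of a control child. A physician may advise it, and the common criteria are open-ended.

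Nor do figures carry the stronger reading. With no true effect, suppose intervention success is only 65% and the step reverses weight loss in 14 of 48 failures, about 30%. Then 41 v 41 becomes 41 v 27, with p = 0.0502 (chi-square, no continuity correction). That share is an assumption without any basis in the protocol, and even this case does not fall below 5%.

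**Conclusion.** The point holds for the withdrawal rule, at minor severity. The cut-off is fixed in the protocol, depends on outcome, can act on any day in either arm, and removes later weights of the sickest children from one of the two sizing outcomes. The size and direction of the bias are unknown, because the protocol gives no expected rate of hospital care and no exact definition of weight loss. The conclusion assumes that follow-up after withdrawal includes weighing, which is the natural reading of *Follow-up*.

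The admission step is a secondary and conditional matter. It is written for the intervention arm only, and it bears on the weight comparison only if weights from about day 14 onward are used. It supports a clarification, not a finding that the arms cannot be compared.

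**What to change.** 1. In *Study withdrawal*, replace the sentence that limits analysis to data before withdrawal with: all collected weights are analysed in the randomised arm regardless of hospital care, except after consent is withdrawn. Add that a child in hospital on a visit day is weighed there.

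2. If weights after about day 14 are to be used, compare weight loss from baseline at the existing day 15 visit, the first after Diet B is complete. Weigh a child admitted under the post-Diet B step before inpatient treatment starts. If that cannot be arranged, use the existing day 13 visit.

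3. Report 4-week weights as a result of the whole strategy including inpatient care. State when that follow-up ends: *Follow-up* says up to 4 weeks, while *Answer to Reviewer # I* says 4 weeks after diarrhoea has resolved.

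The first change is wording plus weighing in hospital, with no new visits or patients. The second shortens the window for the main weight outcome; if only half the planned effect has appeared by day 15, power is 79%. Whether to apply the same admission rule in both arms is for the investigators to decide.
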